Collectively, the prior trials demonstrate the efficacy of RIC on an upper extremity for reducing myocardial infarction. The RIC stimulus varied with respect to the number of cycles used, as well as the remote location used. Concurrent medications including intravenous propofol⁽³⁹⁾ may have attenuated the cardioprotective effect of RIC. Although a mortality benefit was not observed, a minority of patients included in the meta-analysis had a large risk for RI as only 429 (23% of enrolled) patients had acute infarction, and the low risk of mortality in patients undergoing elective CABG, elective PCI or other surgical procedures in the meta-analysis limited detection of a mortality benefit with RIC. No patients with cardiac arrest were enrolled.

SAFETY

Application of medical devices (e.g. BP cuff) to the skin may be associated with adverse local effects such as pain or thrombophlebitis. Importantly, RIC is posited to modify the innate immune system, and so could contribute to infection or mask its diagnosis although no signal has been detected in the clinical trials of RIC. The safety of concurrent use of the autoRIC device in humans who may require defibrillation has not been evaluated.

RATIONALE FOR CURRENT PILOT STUDY

Both OHCA and STEMI share elements of RI with inflammatory changes that contribute to myocardial dysfunction and death,⁽⁹⁴⁾ and RIC may be beneficial in both indications: controlled studies in animal models as well as randomized trials in humans suggest that RIC attenuates RI and reduces infarct size in acute myocardial infarction, and controlled studies in animals suggest that RIC may be beneficial in cardiac arrest.

An automated device has been developed and can easily be applied to patients with OHCA to initiate RIC in the post-resuscitation period. However, the Food and Drug Administration (FDA) has not approved any device for RIC due to the absence of any controlled data demonstrating the benefit of RIC in humans with cardiac arrest. Our Institutional Review Board (IRB) has advised us that demonstration of the feasibility of randomization in the emergency department (ED) setting is necessary before proceeding to an assessment of its effectiveness in the out-of-hospital setting.

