Related to Cardiac Arrest The following are commonly observed in patients who experience cardiac arrest, and may or may not be attributable to specific resuscitation therapies. These will be monitored and reported but not classified as serious adverse events. Clinical diagnoses of pneumonia, cerebral bleeding, stroke, seizures, bleeding requiring transfusion or surgical intervention, rearrest, pulmonary edema, serious rib fractures, sternal fractures, internal thoracic or abdominal injuries as noted in the hospital discharge summary.

Unexpected Adverse Events (UAE)

These will be defined as any serious unexpected adverse effect on health or safety or any unexpected life-threatening problem caused by, or associated with, a device, if that effect or problem was not previously identified in nature, severity, or degree of incidence in the investigation plan or application, or any other unexpected serious problem associated with a device that relates to the rights, safety or welfare of subjects. Death or neurological impairment will not be considered an adverse event in this study, as it is an expected part of the natural history of the illness for a large proportion of the population.

Covariates Key covariates of interest include but are not limited to:

Initial rhythm: (i) VF, vs. (ii) PEA, vs. (iii) asystole, vs. (iv) unknown.

Observational status of arrest:⁽¹⁴⁸⁾ (i) witnessed by EMS, vs. (ii) witnessed by bystanders, vs. (iii) unwitnessed;

Bystander CPR status:⁽¹⁴⁹⁾ (i) performed, vs. (ii) not performed, vs. (iii) unknown.

Response time interval from call to initiation of CPR by EMS:⁽¹⁵⁰⁾ among witnessed cardiac arrests grouped as (i) < 10 minutes, vs. (ii) ≥ 10 minutes.

Gender:⁽¹⁵¹⁾ (i) male vs. (ii) female.

Strata of initial depth of coma:⁽¹²⁴⁾ based on FOUR score.

Strata of initial cardiopulmonary dysfunction:⁽¹²⁵⁻¹²⁷⁾ based on SOFA score.

ANALYSES

Interim Analyses

The data will be monitored regularly by an independent data safety monitoring board (DSMB) to ensure study integrity and patient safety.

Monitoring of Study Conduct

The timeliness, completeness, and accuracy of data entry will be analyzed continuously, with reports provided monthly to the Study Executive Committee. This information will be provided in periodic reports to the DSMB.

Analyses

All outcomes will be summarized descriptively, without statistical comparison as recommended for pilot studies. No claims will be made based on the results of this trial.

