ANALYSIS POPULATIONS

Safety Population

This will include all randomized patients, regardless of initial rhythm and duration of exposure to RIC. Patients will be analyzed within their assigned treatment arm, thereby using an intent-to-treat strategy. This is appropriate given that there are no controlled prior data related to RIC in patients with OHCA. Therefore, we are interested in testing the safety of RIC.

Efficacy Population

This will include all randomized patients whose initial rhythm was VF, regardless of duration of exposure to RIC. Patients will be analyzed within their assigned treatment arm, thereby using a modified intent-to-treat strategy. Note that rhythm is a pre-randomization variable.

SAMPLE SIZE

The null hypothesis is that the attrition rate will be not more than 25%. We assume 59 patients are treated by EMS providers for OHCA (21 due to VF) and have spontaneous circulation upon arrival at the participating receiving hospital annually. We will enroll 30 patients (15 per group) as recommended for pilot studies.⁽¹⁵²⁾ These numbers will allow estimation of accrual with precision (as measured by half-width of 95% CI) of at least 16.8% overall (and 23.7% within each group).

SAFETY AND DATA MONITORING PLAN

Clinical staff will report potential adverse events as soon as possible. The DSMB will review and approve the protocol before the study begins, evaluate rates of outcomes and adverse events throughout the study period, and determine the final monitoring plan. We will forward reports of DSMB recommendations to the FDA, Institutional Review Board (IRB), and sponsoring agencies as required by regulations for human subjects' research.

HUMAN SUBJECT ISSUES

Obtaining informed consent of patients resuscitated from OHCA, or from their legally authorized representative (LAR) is difficult. Patients are in an immediate life-threatening situation with a mortality rate before discharge of about 50%. Since study procedures must be initiated as soon as feasible after restoration of flow to ensure its efficacy,^(72, 153) we will seek approval from the FDA and IRB to conduct the study under exception from informed consent (EFIC) for emergency research.(CFR 50(24)) The initiation of study procedures prior to notification and consent will only apply to the application of the study device.

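### The exclusion of death and neurological impairment from adverse events is wider than its natural-history reason and makes no exception for device-associated cases

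*Protocol*

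**What the plan says.** All the text at issue is in the protocol.

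- **Safety Outcomes, Unexpected Adverse Events (UAE), definition.** Besides serious unexpected adverse effects, a UAE includes "any unexpected life-threatening problem caused by, or associated with, a device", provided it was not previously identified in the plan, and "any other unexpected serious problem associated with a device that relates to the rights, safety or welfare of subjects".
- **Same section, next sentence.** "Death or neurological impairment will not be considered an adverse event in this study". The reason follows: "as it is an expected part of the natural history of the illness for a large proportion of the population".
- **Safety Outcomes, Related to Cardiac Arrest.** A list of complications that includes rearrest and stroke carries the rule "These will be monitored and reported but not classified as serious adverse events".
- **Study Assessments, Monitoring for Outcomes.** Study staff check each patient's record every day for outcomes and possible adverse events.
- **Safety and Data Monitoring Plan.** "Clinical staff will report potential adverse events as soon as possible". The DSMB is to "evaluate rates of outcomes and adverse events throughout the study period" and to settle the final monitoring plan.
- **Secondary and Exploratory Outcomes.** Survival to discharge, survival to 30 days and neurologic status at discharge are all collected.

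**The concern.** The reason and the rule do not have the same reach. In a population where about half die before discharge, it is sensible not to treat every death as an adverse event. That argument applies to deaths and neurological injury that come from the arrest. It gives no ground for excluding a death or impairment judged to come from the device, and the definition one sentence earlier is there to catch unexpected device-associated harm. The exclusion carries no qualifier for cause, and no other section supplies one.

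The trial runs under exception from informed consent, and the Safety Population section gives testing the safety of remote ischemic conditioning as an interest of the study. If the sentence is followed as written, staff who are asked to report potential adverse events are also told that a death is not one, whatever its cause. The most serious form of device-associated harm would then lack the classification that a less serious form receives.

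**Working it through.** The protocol states no figure on this point, so there is none to reproduce. The check has two parts.

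**1. The sentences side by side**

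| Event, assumed unexpected and judged device-associated | UAE definition alone | After the exclusion sentence |
|---|---|---|
| Life-threatening problem, patient survives without neurological impairment | UAE | UAE |
| Death | Falls under the residual clause on other serious device-associated problems | Not an adverse event, so not a UAE |
| Neurological impairment, if serious | UAE | Not an adverse event, so not a UAE |
| Device problem that precedes a death | UAE in its own right | Arguably still a UAE; the protocol does not say, and the death itself stays excluded |

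The second and third rows show the conflict. The fourth shows its limit.

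**2. Whether outcome rates could stand in for classification**

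Inputs: mortality before discharge of about 50% (Human Subject Issues); 30 patients, 15 per group (Sample Size). As an illustration, take deaths per arm as Binomial(15, 0.5).

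- Expected deaths per arm: 15 × 0.5 = 7.5; over both arms 30 × 0.5 = 15.
- Standard deviation per arm: √(15 × 0.5 × 0.5) = √3.75 = 1.94.
- Lower tail: P(X ≤ 3) = (1 + 15 + 105 + 455) / 2^15 = 576 / 32,768 = 0.0176.
- By symmetry P(X ≥ 12) is the same, so P(4 ≤ X ≤ 11) = 1 − 2 × 0.0176 = 0.965. Chance alone gives 4 to 11 deaths in an arm about 96.5% of the time.
- Standard deviation of the difference between arms: √(3.75 + 3.75) = √7.5 = 2.74.
- One additional death moves the expected difference by 1 / 2.74 = 0.37 standard deviations, and two by 2 / 2.74 = 0.73.

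These shifts assume that the device-associated deaths are additional. If some of those patients would have died anyway, the shift is smaller still.

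**The case against.** The best defence is that the two sentences can be read together. The UAE definition attaches to the problem, not to its result. A device-associated collapse would be a UAE when it occurs, and the next sentence only removes death as an event term; it does not say that a UAE ceases to be one if it proves fatal. This reading is available, and it is why the conflict is stated here as holding on a literal reading. But the protocol does not adopt it, and it does not help when death or neurological impairment is the first thing recognised.

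A reader might go further than the text allows in several ways:

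- **That grave harms have no individual report.** Rearrest and stroke lose the serious-event label but are still to be monitored and reported.
- **That the rule removes the only means of detection.** Staff review each record daily, survival is an outcome, the DSMB sees outcome rates, and its final monitoring plan is not shown. Review of individual deaths may be part of that plan, so its absence cannot be asserted.
- **That a nerve injury in the cuffed limb is excluded.** Only a strained reading gives this. The natural-history reason points to brain injury after arrest.
- **That the statement "The safety of concurrent use of the autoRIC device in humans who may require defibrillation has not been evaluated" adds weight.** It concerns the automated device, whereas the Intervention Group section describes a manual cuff and clamp.

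It can also be said that the binomial figures show only how small the trial is, and that no statistical comparison is planned. Both are true. The figures serve one purpose: to show that seeing deaths as rates does not replace judging each one.

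**Conclusion.** The concern holds in a limited form. The exclusion is wider than its stated reason and, read literally, conflicts with the UAE definition before it: a device-associated death or neurological impairment would not itself be classified or reported as an adverse event. Deaths are not lost, because they are recorded as outcomes and the DSMB sees their rates, and a device problem that led to a death might still be reported.

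The remaining gap is case-level classification. The rates do not fill it at this size: one or two device-associated deaths lie well inside the chance variation of an arm with mean 7.5 and standard deviation 1.94. This rests on the protocol's figure of about 50% mortality and on independent outcomes within each arm. It is not sensitive to the exact mortality, since the binomial standard deviation changes little around 50%.

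The protocol should be corrected, and the correction is small. The documents do not show that any device-associated death would in fact go unnoticed.

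**What to change.** Limit the exclusion to match its reason. Suggested wording: *Death or neurological impairment is not an adverse event unless it is judged to be caused by, or associated with, the study device. A relatedness judgement will be recorded for every death. Any death or neurological impairment judged device-associated will be assessed against the definition of an unexpected adverse event given above and reported individually to the DSMB.*

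This leaves the existing definition, including its requirement that the event be unexpected, to decide what counts as a UAE. Making every death during the treatment interval, or every neurological deficit of the cuffed limb, a UAE automatically would go beyond that definition and is not proposed. The second of these would also sweep in arm weakness from a stroke.

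The cost is a short protocol change, one relatedness field for about 15 expected deaths, and a few extra individual reports, some of which may turn out to be natural-history deaths.

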The initial neurological⁽¹²²⁾ and cardiopulmonary status⁽¹²³⁾ upon hospital arrival are important determinants of outcomes after OHCA. Also, the initial degree of cardiopulmonary failure upon hospital arrival is predictive of subsequent development of multi-organ failure. Treating providers will be asked to document neurological status (assessed using the Full Outline of UnResponsiveness [FOUR] score)⁽¹²⁴⁾ and cardiopulmonary dysfunction (assessed using Serial Organ Failure [SOFA] score)⁽¹²⁵⁻¹²⁷⁾ before randomization. These scores are important covariates and will be useful for exploratory secondary analyses.

Documentation of Treatment

This will be assessed as treatment assigned; treatment received; time points used to monitor the time-dependent nature of the intervention including call to 911, sustained restoration of spontaneous circulation (ROSC), initiation of RIC, completion of treatment cycles.

Monitoring for Outcomes

Study staff will review subject's clinical record daily to monitor for outcomes and potential adverse events as well as to monitor use of concomitant treatments.

PRIMARY OUTCOME

Attrition assessed as the proportion of randomized subjects who do not remain on allocated therapy for the intended study duration among subjects randomly allocated. In the intervention group, this will be defined as lack of completion of three cycles of inflation-deflation; In the control group, this will be defined as crossover to the intervention group. Secondary and Exploratory Outcomes

Treatment Success assessed as the proportion of intervention group patients who remain alive and on their allocated therapy for the intended study duration.

Cardiac Function assessed as left ventricular ejection fraction (LVEF) using echocardiograms ordered for clinical indications.

Cardiogenic Shock assessed as systolic BP < 80 mmHg during any 6 h period within 48 h of the index arrest not due to a correctable cause, and treated with pressors or inotropes or placement of a mechanical cardiac assist device (e.g. intra-aortic balloon pump). Cardiogenic shock correlates with survival after resuscitation from cardiac arrest.^(21, 123)

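### Safety is grouped only by assigned arm, so cuff-related events in crossover controls count as sham and never-inflated RIC patients dilute the RIC rate; a supplementary table by treatment received would correct this cheaply

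*Protocol*

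**What the plan says.** Protocol, Analysis Populations, Safety Population, sets membership: "This will include all randomized patients, regardless of initial rhythm and duration of exposure to RIC". It then sets the grouping: "Patients will be analyzed within their assigned treatment arm, thereby using an intent-to-treat strategy". The reason given is that no controlled data on RIC after out-of-hospital arrest exist, and the section ends: "Therefore, we are interested in testing the safety of RIC". No other safety grouping is named.

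Two other sections bear on this rule.

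- Primary Outcome is departure from allocation: "Attrition assessed as the proportion of randomized subjects who do not remain on allocated therapy for the intended study duration among subjects randomly allocated". For the RIC arm: "In the intervention group, this will be defined as lack of completion of three cycles of inflation-deflation". For the sham arm: "In the control group, this will be defined as crossover to the intervention group".
- Documentation of Treatment shows that actual exposure is captured: "This will be assessed as treatment assigned; treatment received", together with the times of RIC initiation and of cycle completion.

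Safety Outcomes lists site pain, thrombophlebitis and infection as the main expected device effects. Specific Aims states that the study will confirm the device's safety for field use.

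**The concern.** The stated purpose is to learn about the safety of RIC. Local harms from a cuff arise in patients who had a cuff inflated, whichever package was opened for them. Grouping by assignment alone misplaces two kinds of patient:

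- A control who crosses over and then has a cuff-related event adds an event to the sham row.
- A RIC patient with no inflation adds a person to the RIC denominator who could not have had a cuff-related event.

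Both errors shrink the apparent difference between arms. The departures that cause them are what the primary outcome counts, so the plan itself allows for them.

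What is at stake is how well the report describes device harm when the next trial is designed. No test result depends on it, since every outcome is summarized descriptively.

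**Working it through.** **The plan's own figures.** The plan gives no figure for safety dilution. Its related figures are on attrition: "The null hypothesis is that the attrition rate will be not more than 25" per cent, 30 patients with 15 per group, and 95% CI half-widths of 16.8% overall and 23.7% per group. The half-widths reproduce as half the width of the exact (Clopper-Pearson) interval at 8/30 (16.80%) and at 4/15 (23.66%). Both are 26.7%, the first whole count above 25%. The plan therefore works around an attrition level near 25%, but it states that value as a bound and not as an expected rate.

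**Inputs that the protocol does not give (assumed).**
- q: risk of a local device event if exposed to RIC
- b: background risk of the same event if not exposed
- a: share of the RIC arm with no inflation at all
- c: share of the sham arm that crosses over to RIC

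The formulas also assume that q and b are the same for adherent and non-adherent patients.

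**Expected rates by assigned arm.**
- RIC arm: (1 − a)q + ab
- Sham arm: cq + (1 − c)b
- Difference: (1 − a − c)(q − b)

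The assigned-arm difference is thus the true difference times (1 − a − c), whatever q and b are.

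| a | c | Factor |
|---|---|---|
| 10% | 10% | 1 − 0.10 − 0.10 = 0.80 |
| 25% | 0% | 1 − 0.25 − 0 = 0.75 |
| 25% | 10% | 1 − 0.25 − 0.10 = 0.65 |
| 25% | 25% | 1 − 0.25 − 0.25 = 0.50 |

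**Illustration with assumed q = 20%, b = 0.** By treatment received, the rates are 20% and 0%.
- At 10% and 10%: RIC 0.90 × 20% = 18%, sham 0.10 × 20% = 2%, difference 16 points.
- At 25% and 25%: RIC 0.75 × 20% = 15%, sham 0.25 × 20% = 5%, difference 10 points.

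With 15 patients per arm, one misplaced event moves an arm's rate by 1/15 = 6.7 points.

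**Partial exposure.** RIC-arm attrition means fewer than three cycles, so a is at most the attrition rate in that arm. Suppose RIC-arm attrition is 25% and half of those patients had one or two cycles that carry the full risk q. Then a = 0.125, and with c = 10% the factor is 1 − 0.125 − 0.10 = 0.775 instead of 0.65. If one or two cycles carry only part of the risk, the factor lies between these two values.

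**The case against.** The strongest reply is that assigned-arm grouping is a deliberate and legitimate choice. It is the only randomized comparison available, and it captures harm from the attempt itself. The protocol worries that applying RIC, at least in the field, may delay other care. Such harm could fall on a patient whose cuff was never successfully inflated. A table of inflation versus none would place that patient on the unexposed side. Patients too unstable for any inflation would go there too, which could make RIC look safer than it is. This objection stands, and it is why the exposure table should not replace or lead the assigned-arm table.

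A second reply is that an extra table belongs in a statistical analysis plan. That is partly right, and such a plan could add it. But the protocol does more than stay silent: it states a grouping rule and justifies it by an interest in the safety of RIC, which that rule serves only in part.

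A third reply is that other provisions cover the gap. Serious unexpected events are defined by their link to a device, whichever arm the patient is in, and an independent board reviews adverse events. This helps, but the unexpected-event definition covers effects not already identified. Pain, thrombophlebitis and infection are listed as expected, so unless unusually severe or frequent they would appear mainly in the assigned-arm summaries.

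Finally, the effect may be small. All six preliminary patients (after arrest or with presumed STEMI) completed three cycles, and no crossover rate is given. With 15 per arm, zero events still leaves an exact 95% upper limit of 1 − 0.025^(1/15), about 22%, so sampling uncertainty is already large. This limits the importance of the point but does not remove it.

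**Conclusion.** The point holds as a modest one. Under the rule as written, local device events in crossover controls are counted as sham, and RIC patients with no inflation lower the RIC rate. The retained share of the true difference is 1 − a − c, for example 0.80 at an assumed 10% each. The documents give no harm rates, no crossover rate and no count of wholly unexposed patients, so the actual size is unknown.

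A reader might infer that half of any real excess of harm would vanish. The documents do not support that. The factor 0.50 needs 25% of RIC patients wholly unexposed and 25% of controls crossed over, whereas 25% is the null bound on attrition and RIC-arm attrition includes patients with one or two cycles.

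A reader might also infer that the assigned-arm analysis is wrong, or that the trial would support a false claim of safety. Neither follows. The assigned-arm table is a valid randomized comparison, and the Analyses section rules out statistical comparison and any claims from the results. What remains is that, taken alone, this grouping describes device harm incompletely in a study meant to confirm device safety.

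**What to change.** Keep the safety population and the assigned-arm table as the randomized comparison. In the Safety Population section, add one supplementary descriptive table of the device-related events (site pain, thrombophlebitis, infection) by treatment received:

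- any RIC inflation versus none, not counting routine blood pressure readings;
- the number of cycles received;
- the assigned arm of each patient, so that crossovers and never-inflated RIC patients are visible.

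A footnote should say that these groups are not randomized and may differ in severity of illness.

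The cost is one extra table. Treatment received, RIC initiation and cycle completion are already recorded under Documentation of Treatment, so no new data are needed and the sample size does not change. The downside is that the exposure groups can mislead if read as a comparison, and for that reason the table should sit beside the assigned-arm table and not ahead of it.

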The control group will have a sham package opened at the bedside as soon as feasible after ED arrival. This will be identical in size, weight and appearance as that in the intervention group, but will contain a sham device. Upon identification that the patient has been randomized to the control group, the care team will proceed with all other resuscitative measures as in the the intervention group.

Initial critical care management of the post-cardiac arrest patient has a large influence on neurological recovery and survival.⁽¹⁰⁰⁻¹⁰⁴⁾ Combinations of hospital-based treatments improve outcomes in patients resuscitated from cardiac arrest compared to historical controls.⁽¹⁰⁵⁻¹¹⁰⁾ Moreover, patients transported to a receiving hospital with a coronary catheterization laboratory tended to have better outcomes versus transportation elsewhere.⁽¹¹¹⁾

Differences in initial care may explain some of the differences in survival rates for subjects admitted to different hospitals after resuscitation from cardiac arrest.⁽⁶⁾ Collectively, these studies demonstrate that hospital-based care of those resuscitated from OHCA impacts patient outcomes and potentially modifies the effect of interventions for cardiac arrest. Thus, experts have recommended a standardized approach to try to achieve optimal outcomes after resuscitation from cardiac arrest.⁽¹¹²⁾ According to this method, protocols for hypothermia-related care and other post-resuscitation care will be mandated via investigator agreements, as well as encouraged through periodic continuing education of hospital staff throughout the study period.

Standard post-resuscitation care will include early application and maintenance of IH followed by controlled rewarming, as is current practice at our institution. We will monitor adherence with IH in hospital, and require remediation if adherence does not meet *a priori* performance standards. Two trials that monitored treatment adherence observed improved outcomes with IH vs. no hypothermia after OHCA.^(29, 113) Earlier initiation of IH after hospital arrival is associated with significantly better survival.⁽¹¹⁴⁾ In contrast, IH without documented achievement of a therapeutic temperature range was not associated with benefit among patients resuscitated from in-hospital arrest.⁽¹¹⁵⁾ There is ongoing equipoise related to the duration and targeted temperature range of IH. In practice, most of our patients receive 24 h of IH targeted to 33°C.

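### By-arm counts of unexpected adverse events depend on a judgement that the event is linked to a device, and the protocol does not require that judgement to be blinded or independent

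*Protocol*

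**What the plan says.** - **What counts.** Under Safety Outcomes, Unexpected Adverse Events (UAE), the definition covers "any unexpected life-threatening problem caused by, or associated with, a device" and, as a further limb, "any other unexpected serious problem associated with a device that relates to the rights, safety or welfare of subjects". Both require a device link. Neither limits the device to the active cuff.
- **How events are found.** The Safety and Data Monitoring Plan says "Clinical staff will report potential adverse events as soon as possible". Under Monitoring for Outcomes, "Study staff will review subject's clinical record daily to monitor for outcomes and potential adverse events". Both routes collect potential events and apply no causality filter.
- **Who knows the arm.** In the Control Group section: "Upon identification that the patient has been randomized to the control group, the care team will proceed with all other resuscitative measures". The control package is matched in size, weight and appearance "but will contain a sham device". The Intervention Group section says staff are trained to apply both active and sham devices. The protocol does not describe what is done with the sham at the bedside.
- **How safety is analysed.** The Safety Population is all randomized patients: "Patients will be analyzed within their assigned treatment arm, thereby using an intent-to-treat strategy". The stated reason is an interest in testing the safety of RIC, given the lack of controlled data in this population. The Analyses section limits reporting to description, with no formal comparison.
- **Who sees it.** The DSMB evaluates rates of both outcomes and adverse events.

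**The concern.** Analysis by assigned arm protects a safety comparison only if events are counted by the same rule in both arms. Here an unexpected event is counted only after a relatedness judgement. The protocol names no assessor and asks for neither blinding nor independence. One arm has a cuff inflated for three cycles; the other has a sham whose use is barely described. The same clinical event may therefore be linked to a device more readily in the RIC arm.

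Two errors could follow:

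- Background events attributed to the cuff could look like an RIC excess.
- A real but unsuspected harm, of a kind on none of the protocol's lists, would be counted in neither arm, so the randomized control could not reveal it.

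Unexpected events are those for which there is least prior knowledge on which to judge causation. They are therefore where a concurrent control helps most.

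**Working it through.** **Plan's own figures.** The protocol gives no UAE rate and no calculation on this point. Its only precision figures (16.8% overall, 23.7% per group) reproduce as exact 95% half-widths at 8/30 and 4/15, but they concern attrition (labelled accrual under Sample Size). The only input used from the protocol is 15 patients per group.

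**Step 1: which events depend on attribution.**

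| Event type | Section | Device link needed? |
|---|---|---|
| Pain (stated for both arms), thrombophlebitis, sepsis | Expected Adverse Events | No |
| Pneumonia, stroke, seizures, bleeding, rearrest, pulmonary edema and the other listed diagnoses | Related to Cardiac Arrest | No |
| Shock, troponin, LVEF, renal dysfunction, neurologic status, survival | Secondary and Exploratory Outcomes | No |
| Serious unexpected events | Unexpected Adverse Events | Yes |

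Only the last row is exposed. A serious event in none of the first three rows and linked to no device has no category.

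**Step 2: illustration on assumed rates.** Let r be the true rate of unlisted serious events, equal in both arms. Let a be the proportion linked to a device in the RIC arm and s the proportion linked in control. The counts are X ~ Bin(15, ra) and Y ~ Bin(15, rs), independent, with expected values 15ra and 15rs. Then

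P(X > Y) = Σ P(X = x) · P(Y ≤ x − 1), for x = 1 to 15.

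If s = 0 this reduces to 1 − (1 − ra)^15. With r = 0.20 and a = 0.50: 1 − 0.90^15 = 1 − 0.206 = 0.794.

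| r = 20% | Expected count, RIC v control | P(RIC > control) |
|---|---|---|
| a = 50%, s = 0 | 1.5 v 0 | 79% |
| a = 50%, s = 5% | 1.5 v 0.15 | 74% |
| a = 50%, s = 25% | 1.5 v 0.75 | 56% |
| a = 50%, s = 50% | 1.5 v 1.5 | 38% |
| All events counted | 3.0 v 3.0 | 41% |

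The last two rows are below 50% because of ties.

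**Step 3: sensitivity to the rate.**

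- r = 10%, a = 30%, s = 0: 0.45 events expected in RIC, and P = 1 − 0.97^15 = 37%. If all events count at r = 10%, P = 38%. On this measure there is no inflation.
- r = 2%, a = 30%, s = 0: 0.09 events expected in RIC, and P = 1 − 0.994^15 = 9%.

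**Step 4: missed harm.** If no unlisted event is linked to a device (a = s = 0), the table shows 0 v 0 whatever the true excess in the RIC arm.

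**The case against.** Three stronger readings are tempting, and the protocol supports none of them.

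1. *The control count is zero by definition.* It is not. The definition speaks of a device, the control package holds a sham device, and staff are trained to apply it. A low control count is plausible, but it is an inference about behaviour. If linkage is equal, so are the expected counts.
2. *Bedside staff who know the arm decide what counts.* The protocol does not say so. Clinical staff report potential events, study staff review records separately, and the person who assesses the device link is not named. The gap is an unnamed assessor with no blinding requirement.
3. *Unrecognised RIC harm goes uncounted.* That is too broad. The harm the Safety section itself raises, contribution to infection or masking of its diagnosis, is largely covered: sepsis and pneumonia are recorded without attribution.

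It is also fair to say that the assumed rates have no source in the protocol. They apply to what remains after death, neurological impairment and every listed diagnosis are set aside, and that remainder may be small. The Specific Aims report more than 12,000 RIC trial patients with no serious adverse events, which does not suggest frequent attribution to the cuff. The analysis is descriptive and claims nothing, and the DSMB sees outcomes as well as adverse events and sets the final monitoring plan.

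These arguments limit the size and reach of the point. They do not remove it: the counting rule is fixed in the protocol, it depends on attribution, and no safeguard for that judgement is stated. A descriptive table can still mislead if its two columns are filled by different rules.

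**Conclusion.** The point holds in a narrow form. By-arm UAE counts rest on a device-relatedness judgement with no stated blinded or independent assessor, in a trial where the care team knows the arm. Serious events that are unlisted and unlinked are counted in neither arm. Listed adverse events and clinical outcomes are not affected.

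The size of the bias cannot be determined from the protocol. On the assumptions of 15 per arm, a 20% true rate in both arms and 50% linkage in RIC, the probability that RIC shows more events ranges from 79% (no control linkage) to 38% (equal linkage), against 41% if all events count. The effect is small if unlisted events are rare. In a 30-patient descriptive pilot this is a minor point, worth correcting because the correction is cheap.

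**What to change.** In the Safety Population and in the DSMB reports, tabulate by assigned arm all serious unexpected events found by the planned daily record review, regardless of suspected device relation. Record device relation in a separate column, name who judges it, and have it judged blinded to arm where possible. Keep the present UAE definition for expedited reporting only.

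The cost is a wording change in the protocol and the DSMB report plus one table. The daily review already covers every subject, so no new data collection is needed. The downside is that more background events will be listed.
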